### **6.3.2 Secondary efficacy analyses**

All secondary efficacy variables given in section 5.3.2 above will be analysed between Exufiber® and Aquacel® Extra on both the PP population and the ITT population according to the statistical methods given in section 6.1. The main analyses will be performed at the 6 weeks follow-up and /or change from baseline to 6 weeks follow-up. For applicable secondary efficacy endpoints last observation carried forward will be applied for the last follow-up measurement before 6 weeks and forward to the final 6 weeks measurement.

Where appropriate, the statistical analyses will also be performed at the 4 week follow-up and /or change from baseline to 4 week follow-up.

For continuous variables and dichotomous variables 95% confidence intervals will be calculated for the mean difference between the two study groups.

Tables with descriptive statistics will be given for all secondary efficacy variables by visit, by treatment group and change from baseline to each visit

### 6.3.3 Subgroups analyses

#### 6.3.3.1 *By country*

Subgroups analyses will be performed by country for primary efficacy variable and for selected secondary efficacy variables.

#### 6.3.3.2 *Interaction analyses*

Exploratory interaction analyses will be performed for primary efficacy variable and selected secondary variables between the two randomized groups and selected baseline variables in order to find subgroups where the effect of Exufiber in relation to Aquacel Extra is significantly improved.

#### 6.3.4 Analyses of 50 subjects long-term study (24 weeks)

Analyses of wound area reduction (compared to baseline) of 80% or more at week 24 and Wound closure (100% epithelialization confirmed by photo) rate between the two randomised groups will be performed with Fisher's exact test for these 50 subjects followed to 24 weeks. 95% confidence intervals for the difference in proportions between the two groups will be given.

All measurement week 8 to 24 will be analysed between the two randomised groups in the same way as secondary efficacy variables in section 6.3.2 above.

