### Ancillary objective

- In order to support that wound area reduction at week 6 is a clinically relevant parameter to predict long-term favorable wound healing, a sub-group of at least 50 subjects will be assessed at 24 weeks post-inclusion. Favorable trajectory will be defined by an area regression, compared to baseline, of 80% or more at week 24. Additionally, wound closure (100% re-epithelialization confirmed by photo) rate will also be evaluated. All these parameters will be centrally measured on photos according to previously described procedure.

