c: Exufiber® or Aquacel Extra should be applied after cleaning/debridement and according to the randomisation schedule. Secondary dressing should be applied according to hospital praxis, simple gauzes of PU films are preferred and active dressings such as anti-microbial dressings are not allowed. Details to be recorded in the eCRF. The ulcer should be treated with a recognized efficient compression system (e.g. multicomponents such as 2,-3- or 4-LB or SSB). Record the nature of applied bandages in the eCRF.

d: Not at week 6/24 (i.e. final visit).

e: The number of dressing changes in-between visits should be captured at each scheduled visit, only changes in the dressing routine will be captured at each scheduled visit.

f: Only at week 4, 6 and 24.

g: Please see Appendix C for a detailed instruction of when photos should be taken.

Please include measuring scale (ruler) with date, subject number and visit number and please respect the confidentiality of the subject by not including any personal numbers or identifying characteristics. A digital camera will be distributed by Mölnlycke Health Care at or before the initiation. The ruler is used for calibration of the photograph for objective measurements in the PictZar program. The PictZar analysis including wound size measurement will be performed on the photos taken after debridement at week 0, 4 and 6 or the final visit if sooner. For subjects that are followed up to 24 weeks, an additional PictZar analysis including wound size measurement will be performed on photos taken at week 24 (or last visit). The PictZar analysis including tissue type measurement will be performed on the photos taken before debridement at week 0, 4 and 6 or the final visit if sooner.

Please refer to Appendix D for a complete digital photography guideline.

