For all secondary endpoints differences between Exufiber® and Aquacel® Extra will be analyzed with the statistical methods given above and 95% confidence interval for the differences between the two groups will be given when appropriate.

The distribution of continuous variables as for changes in continuous variables will be given as mean, SD, median, minimum and maximum and as number and percentages for categorical variables.

Other endpoints will be summarized using descriptive statistics only.

A complete statistical analysis plan (SAP) with the details for all analyses for the whole study will be finalized before first patient in.

A blinded observer will do the measurements of the primary endpoint based on digital photos uploaded in the electronic CRF. The blinded observer will not know the treatment that each subject received.

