## 3. OVERALL DESIGN AND FLOW CHART

Overall Design

The investigation is designed as an open, randomized, non-inferiority, multi-centre investigation. A total of 212 subjects will be randomised. Subjects to be included will suffer from a moderately or strongly exuding venous or mixed ulcer of predominantly venous origin with at least 70% of the wound bed covered with slough at baseline. Both in and out-subjects will be eligible. Each subject will be treated according to the local clinical routine and evaluated during a total treatment period of maximum 6 weeks or until the wound is healed.

At least 50 subjects (from the wound care centers owned by GVW in Germany) out of the total 212 subjects will be followed for maximum 24 weeks to investigate wound closure. Subjects will either be randomized to Exufiber® or Aquacel Extra using a centralized randomization. The secondary dressing will be according to the normal praxis at each clinic and preferably one secondary dressing by treatment group should be chosen to be used for all subjects although no active dressings such as anti-microbial dressings are allowed. Simple gauzes or polyurethane (PU) films are recommended (see schedule of assessment for details). Patients should be treated with a recognized efficient compression system (e.g. multicomponents such as 2-, 3- or 4-LB (two-, three- or four-layer bandage) or SSB (short stretch bandage)). The nature of applied bandages will be captured in the electronic Case Report Form (eCRF).

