### 3.1.1 Schedule of Assessment

Week number	Week 0 (Baseline)	Week 1,2,3,4 and 6	Unscheduled visits*	Week 8-24**
Visit window	NA	± 2 days	NA	± 3 days
Informed Consent	√			
Inclusion and Exclusion Criteria	√			
Subject Demographics including vital signs	√			
Relevant medical condition and surgical procedure	√			
Current treatment	√			
History of Leg ulcer	√			
Wound status (colorimetric scale)	√	√		√
Condition of peri-wound skin	√	√		√
Signs and symptoms of local infection	√	√		
Pain assessment (VAS) a	√	√		
Wound preparation (cleansing b /debridement)	√	√	√	√
Dressing application c	√	√ d	√	√ d
Dressing removal e		√	√	√
EQ-5D-3L	√	√ f		√ f
Photograph g	√	√		√
Clinician's evaluation	√	√		
Subject's evaluation		√		
Technical performance		√		

Week number	Week 0 (Baseline)	Week 1,2,3,4 and 6	Unscheduled visits*	Week 8-24**
Medicine log	↓	↓	↓	↓
Adverse Events	↓	↓	↓	↓

\*: Unscheduled visits can be performed at the clinic if/when deemed necessary for dressing changes. Cleansing should be performed according to intended use. Only saline and warm water or Actimaris Rinsing Solution are allowed on the wound. Debridement is not allowed at unscheduled visits. The dressing log should only be filled in at scheduled visits.

\*\*: At least 50 subjects from the wound care centers owned by GWV in Germany, out of the total 212 subjects, will be followed for 24 weeks or until wound is healed if earlier. Visits will be performed once a month e.g. at week 8, 12, 16, 20 and 24.

a: Document any analgesics used under Medicine Log.

b: Only saline and warm water or Actimaris Rinsing Solution allowed on the wound. Local applications such as pastes and corticosteroids are allowed outside the lesions. Debridement is not allowed at unscheduled visits.

c: Exufiber® or Aquacel Extra should be applied after cleaning/debridement and according to the randomisation schedule. Secondary dressing should be applied according to hospital praxis, simple gauzes or PU films are preferred and active dressings such as anti-microbial dressings are not allowed. Details to be recorded in the eCRF. The ulcer should be treated with a recognized efficient compression system (e.g. multicomponents such as 2-,3- or 4-LB or SSB). Record the nature of applied bandages in the eCRF.

d: Not at week 6/24 (i.e. final visit).

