For the primary efficacy endpoint, and for applicable secondary efficacy endpoints, last observation carried forward will be applied for the last follow-up measurement before 6 weeks and forward to the final 6 week measurement. No other imputation methods will be used.

For the primary efficacy endpoint a sensitivity analysis will be performed using complete case.

Frequency tables (including n, mean, median, standard deviation, minimum and maximum for continuous variables and n, frequency and percentage for categorical values) will be provided for all variables by treatment, as well as for the changes from baseline within each treatment by treatment.

Sub-group analyses by country will be performed.

Exploratory interaction analyses will be performed for primary efficacy variable and selected secondary variables between study groups and selected baseline variables in order to find subgroups where the effect of Exufiber in relation to Aquacel Extra is significantly improved. All statistical tests will be two-sided and conducted at the 5% significance level. All analysis will be performed with SAS software version 9.4 or later.

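### The 24-week sub-group is meant to show that week-6 area reduction predicts long-term healing, but SAP 6.3.4 only compares the two arms and no other section relates week 6 to week 24

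*SAP*

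**What the plan says.** **Purpose.** The ancillary objective appears in the protocol synopsis, protocol section 2 and SAP section 2. It opens "In order to support that wound area reduction at week 6 is a clinically relevant parameter to predict long-term favorable wound healing" and gives this as the reason for assessing at least 50 subjects at 24 weeks. Favourable trajectory means at least 80% area reduction from baseline at week 24. Closure rate is named as an additional evaluation. SAP section 3 gives the closure purpose separately: at least 50 subjects "out of the total 212 subjects will be followed for maximum 24 weeks to investigate wound closure".

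**Analysis.** SAP 6.3.4 covers the 80% criterion and the wound closure "rate between the two randomised groups will be performed with Fisher's exact test for these 50 subjects followed to 24 weeks", with 95% intervals for the difference in proportions between arms. It adds: "All measurement week 8 to 24 will be analysed between the two randomised groups in the same way as secondary efficacy variables" of section 6.3.2. That section is itself a comparison of the two dressings. Protocol 4.8.1 adds only: "Other endpoints will be summarized using descriptive statistics only".

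**Subjects without a week-24 area.** The sub-group "will be followed for 24 weeks or until wound is healed if earlier" (SAP 3.1.1). Note g to the schedule says that "an additional PictZar analysis including wound size measurement will be performed on photos taken at week 24 (or last visit". SAP 6.1 applies last observation carried forward up to the 6-week measurement and then says "No other imputation methods will be used".

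**The concern.** Prediction is a within-subject question: do subjects whose wounds shrink more by week 6 tend to reach at least 80% reduction by week 24? A comparison of arms asks whether the dressings differ at week 24. The second can come out either way whatever the answer to the first.

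The objective is there to support the clinical relevance of the primary endpoint, in a trial that protocol section 1 ties to a reimbursement renewal. If the plan is followed as written, nothing pre-specified addresses it. An analysis added afterwards would leave the form of the predictor, the cut-off, the handling of early healers and the handling of missing week-24 areas open to choice after the data are seen.

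**Working it through.** **1. Is there a linking analysis anywhere?** The sub-group size of at least 50 has no derivation, so there is no planned figure to reproduce. The check is a reading of every analysis section.

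| Place | What it relates |
|---|---|
| SAP 6.3.4 | Arm to week-24 outcome; arm to week 8–24 measurements |
| SAP 6.3.2 (invoked by 6.3.4) | Arm to secondary variables |
| Protocol 4.8.1, SAP 6.1 (logistic regression, covariance analysis) | Arm to outcome, adjusted for baseline variables |
| SAP 6.3.3.2 | Arm by baseline-variable interaction |
| SAP 6.3.5 (Bland-Altman, ICC) | One area reviewer to the other |
| Protocol 4.6.4 and SAP 5.3.2, ancillary endpoints | 80% criterion and closure (the SAP adds EQ-5D-3L), each alone |

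None relates week-6 reduction to week-24 outcome. Separate descriptive summaries of the two do not show prediction either.

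**2. Could the arm comparison answer the question indirectly?** A simulation with assumed inputs: 25 subjects per arm, no arm effect, 30%, 50% or 70% favourable, 4,000 trials per setting, 5% two-sided tests.

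| Latent week-6/week-24 correlation | Fisher test between arms rejects | Week-6 reduction compared by week-24 outcome (Mann-Whitney) rejects | Mean AUC |
|---|---|---|---|
| 0 | about 2–4% | about 5% | 0.50 |
| 0.4 | about 2–3% | 55–60% | 0.68–0.69 |
| 0.8 | about 2–3% | over 99% | 0.88–0.89 |

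The planned test does not respond to the strength of the association.

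**3. What precision could a direct analysis reach?** Inputs: n = 50 (the documents' minimum). The number of favourable outcomes and the AUC are assumptions, since the documents give neither. Hanley-McNeil standard error with n1 favourable and n0 not:

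SE² = [A(1−A) + (n1−1)(Q1−A²) + (n0−1)(Q2−A²)] / (n1·n0), where Q1 = A/(2−A) and Q2 = 2A²/(1+A).

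For A = 0.70: Q1 = 0.5385, Q2 = 0.5765, A² = 0.49. With 20 favourable and 30 not:

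SE² = [0.21 + 19(0.0485) + 29(0.0865)] / 600 = 3.638/600 = 0.00606, so SE = 0.0779, half-width 1.96 × 0.0779 = 0.153, and the interval is 0.55 to 0.85.

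| Favourable v not | Half-width at AUC 0.70 | 95% CI |
|---|---|---|
| 10 v 40 | 0.196 | 0.50–0.90 |
| 15 v 35 | 0.167 | 0.53–0.87 |
| 20 v 30 | 0.153 | 0.55–0.85 |
| 25 v 25 | 0.146 | 0.55–0.85 |

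**4. Wounds already healed or at least 80% reduced at week 6.** For these the association is partly built in, so a sensitivity analysis without them is needed. If 10 events among 40 subjects remain (assumed), SE² = [0.21 + 9(0.0485) + 29(0.0865)] / 300 = 0.01051 at AUC 0.70. The half-width is 0.201 and the interval about 0.50 to 0.90.

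Removing high predictor values also lowers the AUC. Take an equal-variance binormal model with the SAP's SD of 35%, 40% favourable and a mean week-6 reduction of 40% to 60% (the last two assumed). A full-set AUC of 0.80 then falls to about 0.72–0.76, and 0.70 falls to about 0.64–0.67. This is rough: the model puts about 4–13% of subjects above a 100% reduction, which cannot occur.

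**The case against.** **The arm comparison is what the sub-group is for.** This is partly right. SAP section 3 names wound closure as a purpose, 6.3.4 serves it, and those analyses should stay. It would be wrong to infer that 6.3.4 is misdirected as a whole; only the predictive aim is left without an analysis.

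**Supporting an endpoint does not require logistic regression and an AUC.** This stands. A pre-specified correlation or cross-tabulation would also address the objective. The gap is that no such analysis is planned; the model proposed here is one reasonable choice.

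**Fifty subjects are too few.** This stands as a limit on what can be claimed. It is also a reason to fix one analysis in advance and report its interval.

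**The last-visit wording already settles missing week-24 areas.** A reader might infer that it means the healing visit only, from the follow-up rule and the statement that no other imputation is used. The documents do not establish that. SAP 6.3.4 refers to 6.3.2, which contains last observation carried forward, and note g uses similar final-visit wording for the primary endpoint, where carrying forward is planned. Yet the carry-forward rule is worded only for week 6. The point is ambiguous.

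**It can wait, because SAP 6.6 defers the table listings to before the clean file meeting.** That deferral concerns listings and does not provide for new analyses. Protocol 4.8.1 wanted the full SAP before the first patient, the trial is open, and protocol 4.7.3 lets sponsor staff view data once entered. Waiting would not protect against a choice made after seeing the data.

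**Conclusion.** The concern holds as an omission. The plan states a predictive objective and specifies only methods that cannot answer it. This rests on the text of the two documents and on no assumed number.

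Its reach is limited. The objective is ancillary, the closure aim is addressed, and the primary non-inferiority decision does not change. The areas needed are already planned for measurement. The sponsor should correct it, but it does not threaten the main conclusion.

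The precision figures describe the remedy and depend on assumed event counts. At n = 50 with 20 favourable, an AUC of 0.70 carries an interval of about 0.55 to 0.85, so only a moderate-to-strong association could be supported. The restricted set is weaker still. An AUC of 0.80 carried unchanged into it (0.62 to 0.98 with 10 v 30) would look reassuring, but the exclusion itself lowers the AUC, so that reading is too optimistic.

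**What to change.** - **Analysis.** In SAP 6.3.4, pre-specify one analysis pooled over arms and adjusted for treatment: logistic regression of favourable trajectory at week 24 on week-6 percentage area reduction. Report the odds ratio per 10 points and the AUC, each with a 95% CI.
- **Sensitivity.** Repeat it without wounds already healed or at least 80% reduced at week 6.
- **Subjects without a week-24 area.** State one rule. Wounds confirmed healed earlier count as favourable. Show results both with unhealed early leavers counted as not favourable and with them excluded, because keeping early healers while dropping unhealed leavers is asymmetric. Report the number affected. This is a new rule, since the present wording does not settle the matter.
- **Endpoint lists.** Add the predictive measure to the ancillary endpoints in protocol 4.6.4 and SAP 5.3.2.
- **Timing.** Make the change by dated SAP amendment as early as possible, before anyone examines week-24 outcomes against week-6 values.
- **Keep** the between-arm analyses for the closure aim.

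**Cost.** No new data. The work is a SAP amendment, a matching protocol edit and a small set of related models, somewhat more than a single regression. The price is an imprecise estimate, with a sensitivity analysis that may be uninformative (about 0.50 to 0.90 at AUC 0.70 with an assumed 10 events of 40).

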#### 6.3.5 Analysis of agreement between PictZar judgement and French expert.

If inconsistencies are found in the results from the PictZar judgement and the independent French expert then an analysis of agreement between the PictZar judgements and the independent French expert's judgements will be performed with distribution of the differences between the measurements; Bland-Altman Plots, Limits of Agreement and calculation of Intra-class Correlation Coefficient (ICC). The primary efficacy analysis will be done using the PictZar judgments.

## 6.4 Safety

All safety variables will be summarized and analysed descriptively by treatment group on the safety population.

The number of subjects reporting one or more AE/ADE/SAE/SADE/DD will be summarised by treatment group using frequency counts. If very few AE/ADE/SAE/SADE/DD these will only be listed.

The incidence (%) of AE/ADE/SAE/SADE/DD reported during the investigation will be summarised in an overview table and by treatment group.

## 6.5 Determination of Sample Size

This investigation was designed to document the non-inferiority of the test dressing, Exufiber®, compared with the control dressing, Aquacel® Extra, on the relative reduction/change in wound size from baseline to end of investigation (6w). Applying a non-inferiority margin of 12% (same as EARTH investigation, Meaume et al 2014) and a standard deviation of 35%, 106 subjects were necessary in each group (i.e. 212 subjects in total) with

a power level at 80%. Two investigations have previously been conducted on Exufiber®, one on diabetic foot ulcer and one on pressure ulcer. The SD are a little higher than 35% but since those investigations were quite small (21 subjects) it is reasonable to expect a smaller SD which justifies the calculation above.

## **6.6 Listings of Tables, Figures and Listings**

### **6.6.1 Listing of Tables**

Will be defined before clean file meeting.

### **6.6.2 Listing of Figures**

Will be defined before clean file meeting

### **6.6.3 Listings of Listings**

Will be defined before clean file meeting

[figure not shown]
